### 2.3 Sample size

See section 5.1 of the protocol, under “Sample size calculation for the RCT”. The calculated sample size includes a total of 274 patients (137 in each arm, and in 12 clusters in total).

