## 6.2 Analysis methods

### 6.2.1 Primary analysis

The primary analysis will be an intention-to-treat analysis to compare the life-space assessment (LSA) between intervention and control groups at D30. LSA will be analyzed using GEEs with Gaussian distribution, exchangeable correlation structure and robust standard errors with small sample correction. This model accounts for the cluster design as well as for the small number of clusters and will be adjusted for the baseline LSA. The absolute difference between intervention group and control group will be presented with a 95% confidence interval (CI).

Continuous secondary outcomes will be evaluated likewise, adjusting for the baseline value if applicable. If outcome measures are non-normally distributed, we will apply an adequate distribution in GEE (e.g., gamma) or log-transform the outcome measure before analysis. Absolute differences between intervention group and control group will be presented with a 95% CI.

Binary outcomes will be analyzed using a GEE with a binomial distribution, a logit link, an exchangeable correlation structure and robust standard errors. Relative differences between groups will be presented as odds ratio with 95% CI.

Count outcomes will be analyzed using a GEE with a negative binomial distribution, a log link, an exchangeable correlation structure and robust standard errors. Relative differences between groups will be presented as rate ratio with 95% CI.

Time-to-event outcomes will be analyzed using a Cox regression model. To account for clustering, we will use shared frailties for clusters as well as cluster robust standard errors. Relative differences between groups will be presented as hazard ratio with 95% CI.

Categorical outcomes (discharge destination) will be analyzed using multinomial logistic regression with robust standard errors to account for clustering. Relative differences between groups will be presented as rate ratios with 95% CI.

Readmissions and emergency room visits will be analyzed as time-to-event outcomes, except if we notice that those outcomes often happen multiple times. In such case, we will analyze them as count outcomes.

Mortality and time to new institutionalization will be analyzed as time-to-event.

Falls will be analyzed as binary outcomes. If we notice that this outcome often happens multiple times, we will analyze it as a count outcome.

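### The Cox analysis of the time-to-event outcomes stacks a ward frailty and an uncorrected cluster-robust variance, with only 12 wards and no single method named as primary

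*SAP*

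**What the plan says.** SAP section 6.2.1 states: "Time-to-event outcomes will be analyzed using a Cox regression model". To handle clustering, the next sentence adds that "we will use shared frailties for clusters as well as cluster robust standard errors". The result is reported as follows: "Relative differences between groups will be presented as hazard ratio with 95% CI". The SAP gives no frailty distribution, no small-sample correction and no reference distribution for this model.

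The same section always assigns death and new institutionalization to this analysis. Readmissions and emergency room visits are also assigned to it, unless they recur often enough to be analysed as counts.

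The primary outcome is specified more fully: "LSA will be analyzed using GEEs with Gaussian distribution, exchangeable correlation structure and robust standard errors with small sample correction". The SAP gives its reason: "This model accounts for the cluster design as well as for the small number of clusters". Continuous secondary outcomes follow the same approach. Section 2.3 gives the size of the trial: "a total of 274 patients (137 in each arm, and in 12 clusters in total").

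**The concern.** A shared frailty puts the ward effect into the model, and the fit then supplies its own model-based variance. A cluster-robust (sandwich) variance is normally paired with a Cox model without frailty, where it repairs a variance computed as if patients were independent. Section 6.2.3 treats the corresponding pair for the other outcomes, mixed models and GEEs, as alternatives. Only the Cox paragraph asks for both together.

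Two things follow.

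- The variance behind the reported confidence interval is not fixed. It could be the sandwich on the frailty fit, in one of several forms, or one of two separate analyses with neither named as primary.
- Wherever the sandwich is used, it rests on 12 ward-level contributions. Uncorrected, such a variance is biased downwards, and a normal reference adds to the problem. The SAP recognises this for the life-space analysis but does not carry it over.

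At stake are the confidence intervals and tests for death, new institutionalization and probably readmissions and emergency room visits.

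**Working it through.** **Inputs from the SAP.** 274 patients and 12 wards (2.3), 1:1 allocation of wards (2.1), two-sided 5% level (4.1). Arithmetic: 274/2 = 137 per arm, which agrees with the SAP, and 274/12 = 22.8 patients per ward. The basis of the 274 is left to the protocol and is not needed here.

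**Assumptions (the SAP gives no figures).** Six wards per arm, 22 to 23 patients per ward, event risk by day 180 of 15% or 35%, log-normal ward frailty with variance 0, 0.05, 0.1 or 0.2, no treatment effect. Randomization strata and unequal ward sizes were not simulated.

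**Step 1: reference distribution alone.** With K = 12 wards and two arms, the degrees of freedom are 12 − 2 = 10. The two-sided 5% critical value of t(10) is 2.228, against 1.960 for the normal. Using 1.960 where t(10) applies gives P(|t(10)| > 1.960) = 7.8%, even if the variance is unbiased.

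**Step 2: simulated type I error.** 1,500 null trials per row; nominal value 5%. The Monte Carlo standard error near 10% is √(0.10 × 0.90/1500) = 0.8 points, and near 5% it is √(0.05 × 0.95/1500) = 0.6 points.

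| Frailty variance | Event risk | A: no frailty, uncorrected sandwich, z | B: no frailty, sandwich variance × K/(K−2), t(10) | C: frailty, model-based SE, z | D: frailty + sandwich, penalised scores, z | E: frailty + sandwich, unpenalised scores, z |
|---|---|---|---|---|---|---|
| 0 | 15% | 9.1% | 4.7% | 2.1% | 9.1% | 15.3% |
| 0 | 35% | 10.7% | 4.1% | 2.8% | 10.5% | 18.9% |
| 0.05 | 15% | 10.0% | 4.9% | 3.1% | 10.1% | 18.9% |
| 0.05 | 35% | 10.3% | 5.4% | 4.2% | 10.3% | 26.5% |
| 0.1 | 15% | 9.9% | 4.5% | 4.3% | 9.8% | 22.3% |
| 0.1 | 35% | 9.0% | 4.5% | 5.5% | 9.1% | 33.5% |
| 0.2 | 15% | 11.5% | 4.7% | 5.7% | 10.7% | 29.6% |
| 0.2 | 35% | 10.1% | 4.7% | 6.7% | 9.7% | 46.7% |

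Columns D and E are the literal reading of the SAP: one model with both devices. They differ only in whether each ward's score contribution includes the frailty penalty term. Columns B and C each use a single method.

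A further set of 3,000 null trials per setting (frailty variance 0 or 0.05) gave 9.0 to 10.0% for A and 4.1 to 4.8% for B. With the uncorrected sandwich and t(10), the rate was 6.0 to 6.5%, so the t reference alone does not quite restore 5%.

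**Step 3: can the combination be fitted?** Section 6.7 allows R 4.2 or higher. In R 4.3.3 with survival 3.8.3, the standard Cox function was given simulated data of 12 wards of 23 patients. It ran with the frailty term alone and with the cluster term alone, and stopped with an error when given both. This says nothing about Stata or other R packages.

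**Step 4: cost of correction (B against A).** The standard error grows by √(12/10) = 1.095 and the critical value by 2.228/1.960 = 1.137. The interval on the log hazard scale is therefore 1.095 × 1.137 = 1.245 times as wide.

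**The case against.** Several points on the other side are sound.

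- **The combination is not illegitimate in principle.** A sandwich on a frailty fit can be defended as protection against a wrong frailty distribution. That is fair, but the sandwich still draws on 12 wards, and column D shows that the extra layer moves the error rate away from 5% compared with column C.
- **The wording may mean two analyses.** On that reading the frailty analysis with its model-based standard error rejects in 2.1 to 6.7% of null trials, so it would be wrong to say that every interval is too narrow. The defect is then that neither analysis is named as primary.
- **The missing correction is not peculiar to the Cox model.** Section 6.2.1 names none for the binary, count and multinomial models either. What is specific here is the pairing of the two devices.

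A reader might also infer that the meaning of the hazard ratio is unclear or depends on the software. The SAP does not support this. A robust standard error leaves the estimate unchanged, and with a frailty in the model the hazard ratio is conditional on ward.

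Nor is a conditional hazard ratio a practical problem. Assume a gamma frailty with variance θ, a conditional hazard ratio of 0.70 and a cumulative control hazard of −ln(0.65) = 0.43. The marginal hazard ratio at day 180 is 0.70 × (1 + 0.43θ)/(1 + 0.70 × 0.43θ). This is 0.704 for θ = 0.05 and 0.717 for θ = 0.2, a shift of under 1% and about 2.5%.

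It is also tempting to say that the Cox results should be marginal because every other outcome is analysed by GEE. Discharge destination is not: it uses multinomial regression. Section 6.2.3 also makes a mixed model primary where a GEE fails to converge. A marginal Cox model is therefore a preference, not a requirement.

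**Conclusion.** The point holds as a defect in the variance and in the naming of a primary method. It is limited to the secondary time-to-event outcomes; the primary life-space analysis carries its correction and is not touched.

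Read as one model, the stated rule gives a type I error of about 9 to 11% when the sandwich is computed with the penalty included, roughly twice the nominal level. It gives 15 to 47% when the penalty is left out. A careful programmer would avoid the second form, but the SAP does not exclude it. The figure near 10% was stable over all eight settings. The 15 to 47% range rises with the assumed frailty variance and should be read as showing dependence on an unstated choice, not as a forecast.

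All rates rest on the assumed event risks, frailty variances and equal wards. The frailty model was fitted with the same type of frailty that generated the data, which favours column C.

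**What to change.** In section 6.2.1, name one primary clustering method for the Cox outcomes, with its variance and reference distribution. Either of these is defensible:

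- **(a)** a Cox model without frailty, with a ward-robust standard error carrying a small-sample correction (for example, variance multiplied by K/(K−2) with K = 12 wards) and a t reference on 10 degrees of freedom; simulated type I error 4.1 to 5.4%; or
- **(b)** a shared-frailty Cox model with its model-based standard error, the frailty distribution stated, and the hazard ratio labelled as conditional on ward; simulated type I error 2.1 to 6.7%.

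Keep the other as a sensitivity analysis, in parallel with the mixed models in section 6.2.3. Option (a) stays closer to 5% over the settings tried; option (b) is conservative when wards hardly differ.

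The change costs a sentence or two in the SAP and no extra data. The price is wider intervals: under (a), about 25% wider on the log hazard scale than an uncorrected sandwich with a normal reference.

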10) Hand-grip muscle strength at hospital discharge	Muscle strength	strength_dynamo1_discharge, strength_dynamo2_discharge, strength_dynamo3_discharge	Continuous	Best of three attempts
11) Level of activity during hospitalization (% in light, moderate, [very] vigorous)	Accelerometer output	accelero_activity_level [% in light activity], acelero_activity_level_2 [% in moderate activity], acelero_activity_level_3 [% in (very) vigorous activity]	Continuous	Continuous
12) Level of activity during hospitalization (intensity of movement: vector magnitude CPM)	Accelerometer output	Accel_vm_cpm	Continuous	Continuous
13) Fear of / concerns about falling at discharge, D30 and D180	Falls Efficacy Scale – International	fes_i_total_d30/d_180	Continuous [range 16-64]	Continuous
14) FRID prescribing at hospital discharge	Medication classes at discharge	med_frid_discharge	Binary (Yes/No)	Binary (yes/no)
15) FRID prescribing at hospital discharge, D30 and D180	Medication classes at D30-D180	med_frid_discharge_fu_d30, med_frid_discharge_fu_d180	Binary (Yes/No)	Binary (yes/no) and

16) Falls during hospitalization and within D30 and D180	Falls	falls_yn_discharge1 / falls_yn_d301 / falls_yn_d180 (1 => repeated instrument);	Binary (yes/no)	Sum the number of falls for the count analysis	Binary (yes/no) or count
17) New institutionalization at hospital discharge and within D30 and D180	New institutionalization	new_institutionaliza_v_11_d30/d180 instit_date_d30/d_180	Binary (Yes/No) Date		Time- to event
18) Discharge destination	Index hospitalization – discharge data	Discharge_destination	Categorical [home, family (not own home), rehabilitation, nursing home permanent, nursing home temporary, other hospital, other institution, acute geriatrics, palliative ward, same hospital other ward, ICU, death, other]		Categorical
19) Emergency room visits within D30 and D180	Emergency room visits	er_visit_yn_30d1 (1 => repeated instrument); for between D30 and D180: same variable with “_180” instead of “_30” Date: er_visit_date_30d1 / _180d1	Binary (yes/no) Date	Sum the number of readmissions for the count analysis	Time-to-event or count
20) Readmissions within D30 and D180	Readmissions	readmission_yn_30_d1 (1 => repeated instrument); for between D30 and D180: same variable with “_180” instead of “_30” Date: readmission_30d1 / _180d1	Binary (yes/no) Date	Sum the number of readmissions for the count analysis	Time-to-event or count

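### Discharge destination: a multinomial model on 13 ungrouped levels reports misnamed rate ratios, with no reference category, no rule for sparse levels and no small-sample correction

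*SAP*

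**What the plan says.** - **Outcome.** SAP section 6.1, Table 2, item 18 defines discharge destination as a categorical variable. Its levels are "home, family (not own home), rehabilitation, nursing home permanent, nursing home temporary, other hospital, other institution, acute geriatrics, palliative ward", followed by "same hospital other ward, ICU, death, other". That is 9 + 4 = 13 levels. No grouping is given.
- **Model.** Section 6.2.1: "Categorical outcomes (discharge destination) will be analyzed using multinomial logistic regression with robust standard errors to account for clustering".
- **Effect measure.** The next sentence reads "Relative differences between groups will be presented as rate ratios with 95% CI". No reference category is named. In the same section, logit models for binary outcomes report odds ratios. The negative binomial model for counts carries almost the same sentence as this one: "Relative differences between groups will be presented as rate ratio with 95% CI".
- **Size.** Section 2.3: "The calculated sample size includes a total of 274 patients (137 in each arm, and in 12 clusters in total").
- **Small-sample correction.** Section 6.2.1 states one for the Gaussian GEE, citing the small number of clusters. It states none for the multinomial model.
- **Rules that might have helped.** Section 6.4 combines levels below 5%, but only for variables in the imputation models. Section 6.2.3 gives a fallback for non-convergence, but only for GEE models.

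**The concern.** There are three problems, and an analyst following the text would meet all of them.

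1. The reported quantity would carry the wrong name. A reader told that the rate ratio for rehabilitation is 0.77 will take it that 23% fewer patients went there. The model does not say that, because its ratio also moves when the share in the reference category moves.
2. Thirteen levels in 274 patients leave many levels with a handful of patients. A level seen in one arm and not in the other has an infinite estimate and no usable interval. The SAP has no rule for this outcome, so any grouping would be chosen once the data are in view.
3. Robust standard errors from 12 wards, used without correction, give intervals that are too narrow.

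**Working it through.** **Inputs from the SAP.** 13 levels (Table 2, item 18); 274 patients, 137 per arm, 12 wards (section 2.3); 1:1 ward allocation in blocks of two (sections 2.1 and 2.2), taken as 6 wards per arm with 22-23 patients each; two-sided 5% tests and 95% intervals (section 4.1). The SAP's own arithmetic agrees: 2 × 137 = 274. It gives no destination frequencies, and no ICC for this outcome, so both are assumed below.

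**1. What the model estimates.** For destination k and reference r, the exponentiated arm coefficient is

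[P(k | intervention) / P(r | intervention)] ÷ [P(k | control) / P(r | control)].

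No count or person-time enters. Two assumed examples, with home as reference:

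- Home 60% to 66%, rehabilitation 20% to 17%: model (0.17/0.66)/(0.20/0.60) = 0.77; ratio of proportions 0.17/0.20 = 0.85.
- Home 70% to 60%, rehabilitation 15% to 22%: model (0.22/0.60)/(0.15/0.70) = 1.71; ratio of proportions 0.22/0.15 = 1.47.

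**2. Number of parameters.** Unadjusted: 12 intercepts + 12 arm effects = 24. Section 6.2.3 adjusts each model for seven listed items (eight if ADL and IADL limitations count separately). Applied here, that gives 12 × (1 + 1 + 7) = 108 or 12 × (1 + 1 + 8) = 120 parameters for 274 patients.

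**3. Empty levels.** A level with true share p in both arms is absent from one given arm with probability e = (1 − p)^137. It is absent from exactly one arm with probability 2e(1 − e).

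| True share p | Expected per arm | Empty in exactly one arm |
|---|---|---|
| 0.5% | 0.7 | 50% |
| 1% | 1.4 | 38% |
| 2% | 2.7 | 12% |
| 3% | 4.1 | 3% |
| 5% | 6.9 | 0.2% |

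The chance that at least one of the 13 levels is empty in exactly one arm was then found for several assumed distributions, ignoring clustering:

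- **Home 60%, rehabilitation 15%, the other 11 levels sharing 25% evenly.** Each has p = 25%/11 = 2.27%, so e = 0.0429 and 2e(1 − e) = 0.0821. Treating levels as independent, 1 − (1 − 0.0821)^11 = 61%. Multinomial simulation gives 61-62%.
- **Home 60-75%, rehabilitation 10-15%, several levels at 0.5-2%.** Simulation gives 89% (home 60%), 95% (home 70%) and 97-98% (home 75%).
- **Home 40%, the other 12 levels at 5% each.** 2%.
- **All 13 levels equal.** Under 1%.

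Clustering raises these figures. With ICC 0.02 the second case becomes 93-99% and the third 7%.

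**4. Uncorrected robust standard errors.** Simulation under no effect, with 6 wards per arm, beta-binomial or Dirichlet-multinomial ward variation, ICC 0.02 and 0.05, and rejection when the robust |z| exceeds 1.96:

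- binary log odds ratio, true share 20%, 35% or 60%: type I error 10.0-10.6%;
- multinomial contrast of rehabilitation (15%) with home (60%): 10.2-10.5%;
- the same tests with the robust variance scaled by 6/5 and a t reference on 10 degrees of freedom: 4.7-5.0%.

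Scaling the variance by 12/11 alone still leaves about 9%.

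**The case against.** The strongest reply is that the model can be fitted. A reader might infer from 13 levels, 274 patients and 12 wards that it is not estimable at all, or that some coefficients are bound to be infinite. The SAP does not support either. Every contrast whose level and reference occur in both arms has a finite estimate, and a level absent from both arms drops out. Only a level absent from exactly one arm gives an infinite estimate. How often that happens depends on frequencies the SAP does not state, and the range above runs from under 1% to 98% without clustering. This part of the reply stands.

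A reader might also say that the overall test fails. With 6 wards per arm the ward contributions sum to zero within each arm, so the robust variance has rank at most (6 − 1) + (6 − 1) = 10. A joint test of 12 arm effects could not be computed with all 13 levels in use. But the SAP plans no joint test for this outcome. It promises ratios with intervals, and those exist for single contrasts. The rank limit is therefore no defect of the plan as written.

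Two further points are fair. The missing small-sample correction also affects the binary and count models in section 6.2.1, so it is not peculiar to this outcome. And discharge destination is one of 22 secondary outcomes; new institutionalization (item 17) and death (item 21) are analysed separately.

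None of this answers the wrong name, the missing reference category or the absence of a rule for sparse levels. A very even spread of destinations is also the less plausible case: levels such as ICU, palliative ward and death are likely to be small in community-dwelling, ambulatory patients with end-of-life excluded (section 5.2).

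**Conclusion.** The point holds in this form.

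- **Certain, with no assumption:** rate ratio is the wrong name for what the model gives; no reference category is fixed; 13 levels enter ungrouped; and neither the combining rule in section 6.4 nor the fallback in section 6.2.3 covers this outcome.
- **Likely, conditional on frequencies:** at least one infinite or very unstable contrast. The chance is about 61-62% under an even spread of the minor levels and 89-98% if several hold 0.5-2%, but only about 2% if every level holds at least 5%.
- **Conditional on an ICC of 0.02-0.05 and on the robust z-test being used as written:** about 10% type I error at a nominal 5%, so nominal 95% intervals cover about 90%.

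The text should be changed, but the issue is confined to one secondary outcome. The primary analysis does not depend on it.

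**What to change.** Amend item 18 of Table 2 and the sentences on categorical outcomes in section 6.2.1 before unblinding.

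1. **Preferred.** Make the between-arm comparison home or family versus any other destination, using the binary GEE already in section 6.2.1 and reporting an odds ratio. Add small-sample-corrected robust standard errors and a t reference. Tabulate all 13 codes by arm without testing.
2. **If a multinomial model is kept.** Collapse to a few exhaustive groups that place every code, including palliative ward, ICU and death. Four groups would need 2 × 3 = 6 parameters unadjusted instead of 24. Add a rule for merging sparse groups, applied to pooled blinded data: a group holding 1% of patients would still be empty in exactly one arm 38% of the time. Name home as the reference, report relative risk ratios, and use the same correction and t reference.

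The cost is SAP wording only. The downside is that rare destinations are described and not tested, but with 137 patients per arm they could not be tested usefully anyway.

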### 6.2.2 Secondary analyses

The secondary analyses will be analyses of primary and secondary outcomes on the PP set.

### 6.2.3 Sensitivity analyses

We will use generalized linear mixed-effects models instead of GEEs to account for clustering. For outcomes measured at D30 and D180, we will use a repeated-measures mixed-effects model. Should a GEE model not converge, we will use a mixed-effects model for that specific outcome as the primary analysis approach.

Because cluster randomization may lack the excellent balancing in characteristics between groups seen in individual-level randomization, we will adjust each model for additional pre-defined patient-level variables (age, sex, body mass index, LSA, number of ADLs/IADLs limitations, fear of / concerns about falling and muscle strength at baseline) to account for case-mix differences between groups in a sensitivity analysis. Moreover, we will assess imbalances of patient characteristics between groups. If we observe imbalances in covariates not considered in the sensitivity analysis, we will perform additional adjustments to assess the robustness of our results.

